10. ASSESSMENT OF SAFETY

10.1 Adverse Events

10.1.1 Reporting Adverse Experiences

Any AE (clinical sign, symptom, or disease) temporally associated with the use of this investigational drug, whether or not considered related to the investigational product, shall be documented on the CRF and eDC. All SAEs and AEs reported by the subject or observed by the Principal Investigator for up to 30 days after the last dose of study medication will be individually listed. The signs and symptoms, time of onset (24-hour clock), duration, action taken and follow-up procedures will be reported.

10.1.2 Definitions

Adverse Event – Any untoward medical occurrence in a clinical investigation subject administered a drug and does not necessarily have a causal relationship with this treatment. An AE can therefore, be any unfavorable and unintended sign (including an abnormal laboratory finding), symptom, or disease temporally associated with the use of an investigational product, whether or not related to the investigational product.

Serious Adverse Event (SAE) – An adverse drug experience that results in any of the following outcomes: death, a life-threatening experience, requires or prolongs subject hospitalization, results in persistent or significant disability/incapacity, or is a congenital anomaly or birth defect.

Cases of liver transaminases that increase above 3 times the upper limit of normal must be reported as SAEs regardless of whether the above defined SAE criteria are met.

Unexpected Adverse Event: Any adverse event that is not identified in nature, severity, or frequency in the current Investigator's Brochure.

Additionally, the Principal Investigator will evaluate all AEs as follows:

Action taken: whether or not the AE caused the subject/patient to discontinue the study medication.

Intensity, to be graded as:

DEGREE	DESCRIPTION
Mild	Awareness of signs and symptoms; easily tolerated
Moderate	Discomfort sufficient to interfere, but not prevent daily activity
Severe	Unable to carry out usual activity

Relationship to study medication, to be graded as:

DEGREE	DESCRIPTION
Definitely	There is evidence of exposure to the study drug, for example, reliable history or acceptable compliance assessment; the temporal sequence of the AE onset relative to the medication is reasonable; the AE is most likely to be explained by the treatment than by another cause; the AE shows a pattern consistent with previous knowledge of the treatment.
Probably	There is evidence of exposure to the study drug; the temporal sequence of the AE onset relative to medication administration is reasonable; the AE is more likely explained by the treatment than by another cause.
Possibly	There is evidence of exposure to the study drug; the temporal sequence of the AE relative to the medication administration is reasonable; the AE could have been due to another equally likely cause.
Probably not	There is evidence of exposure to the study drug; there is another more likely cause of the AE.
Definitely not	The subject/patient did not receive the study drug; or temporal sequence of the AE onset relative to administration of the study drug is not reasonable; or there is another obvious cause of the AE.

10.1.3 Serious Adverse Events (SAEs)

The Principal Investigator shall document all SAEs in a subject receiving study drug until completion of the study and must be reported to the Repros Therapeutics Inc. Safety Monitor within 24 hours by Fax or telephone, even if the SAE does not appear to be drug-related. This report should include all available information at the time of notification. This notification should be followed with submitting a SAE Report Form provided by Repros Therapeutics Inc, and notifying the IRB.

All additional follow-up reports must be reported to the Repros Therapeutic Inc. monitor as soon as available.

Cases of liver transaminases that increase above 3 times the upper limit of normal must be reported as SAEs regardless of whether the above defined SAE criteria are met.

11. CONCOMITANT MEDICATIONS

11.1 Prohibited Medications

The following medications are prohibited during the study:

- Testosterone
- Progestin
- Androgen
- Estrogen
- Anabolic steroids
- DHEA
- Other hormonal products
- Any other treatment for uterine fibroids

11.2 Other Medications Taken During the Study

Any other prescription or over-the-counter medication taken during the study will be recorded in the appropriate section of the CRF. Subject must be on a stable dosage of approved concomitant medications at least 48 hours prior to drug administration.

12. STATISTICAL METHODS

12.1 Determination of Sample Size

This is a extension study and the number of subjects will be dependent on the number of subjects completing the parent studies. No more than 60 subjects are expected to enroll.

12.2 Statistical and Analytical Plan

Analyses in this study will focus on comparison to two baseline assessments. One baseline is associated with the original parent study baseline and the other is associated with the 28-day period prior to the start of this extension study. Reference to baseline in this section refers to each baseline definition.

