12.2.3 Percentage Change in PBAC Scores

The percentage change in PBAC scores over each 28 day period of the course will be recorded and compared to baseline to determine onset of benefit. Additionally PBAC scores will be used to monitor the level of vaginal bleeding during the ODI.

Within treatment group paired t-tests will evaluate treatment effect. While the primary assessment will be after each 18 week treatment course, summaries will be prepared for each of the other visits. If data are missing, a last observation carried forward procedure will be used, including the baseline, if necessary. Non-parametric methods will be employed as appropriate.

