12.2.4 Percentage Change in Total and Individual Symptom Severity Scores for the UFSQOL

The UFSQOL has been validated as a three month look back

questionnaire. The survey will be administered at baseline and at the end of each course. Within group paired tests will be used to assess treatment effect. Non-parametric methods will be employed as appropriate. If data are missing, a last observation carried forward procedure will be used, including the baseline, if necessary.

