12.2.5 Percentage Change in Uterine Fibroid Volume by MRI

The percent change from baseline in total uterine fibroid volume will be determined at the end of treatment. This study will assess up to 3 fibroids present at baseline in each subject. The volume of these 3 fibroids will be summed to determine the total uterine fibroid volume at each assessment.

Within group paired tests will be used to assess treatment effect. Nonparametric methods will be employed as appropriate. If data are missing, a last observation carried forward procedure will be used, including the baseline, if necessary.

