12.3 General Statistical Issues

A Statistical Analysis Plan (SAP) will be finalized prior to unblinding the study. For the efficacy variables a last observation forward approach will be used to impute missing data to generate a complete ITT data. If there are no post-baseline efficacy data then a value of no change will be imputed for the

missing efficacy measure. Statistical significance will be declared if the twosided p-value is ≤ 0.05 .

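### Does calling change from both the parent-study baseline and the extension baseline a treatment effect require a change to the plan?

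*Combined protocol and SAP*

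**What the plan says.** Section 12.2 defines a parent-study baseline and adds that "the other is associated with the 28-day period prior to the start of this extension study". It then applies both throughout: "Reference to baseline in this section refers to each baseline definition".

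Three efficacy sections inherit this:

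- **PBAC (12.2.3):** "The percentage change in PBAC scores over each 28 day period of the course will be recorded and compared to baseline", and "Within treatment group paired t-tests will evaluate treatment effect".
- **UFS-QOL (12.2.4):** "The UFSQOL has been validated as a three month look back" questionnaire, given at baseline and at the end of each course. "Within group paired tests will be used to assess treatment effect".
- **Fibroid volume (12.2.5):** "Within group paired tests will be used to assess treatment effect. Nonparametric methods will be employed as appropriate".

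Section 12.3 sets the threshold: "Statistical significance will be declared if the twosided p-value is" at most 0.05. Amenorrhea (12.2.2) uses no baseline and is not involved.

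Section 8.1 names both baselines for the UFS-QOL Symptom Severity score and for fibroid volume. It lists change for UFS-QOL and PBAC, and percentage change for fibroid volume. Section 8.2.1 enrols parent-study completers for continued treatment. Entry is at parent Visit 24, or at Visit 19 for women who did not reach amenorrhea. Section 8.2.3 states that there is no randomization, and Section 7 makes safety the primary objective.

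**The concern.** One label covers two quantities. Change from the parent baseline is cumulative. Change from the extension baseline starts from a state that parent treatment may already have improved. The usual entry route, Visit 24, is for women who met the amenorrhea definition during the parent study, so retained benefit is a reasonable expectation in those who took active drug.

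The UFS-QOL looks worse still. A three-month recall completed at entry reaches well past a 28-day window and could cover days on parent drug. Sections 12.2.3 and 12.2.4 also analyse percentage change where Section 8.1 lists change, and a percentage depends on which baseline is the denominator.

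At stake is interpretation. A non-significant change from the extension baseline could be reported as no effect when it shows maintained benefit. The readable text does not say which test governs if the two disagree.

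**Working it through.** The plan gives no effect size, SD or power for these tests. Section 12.1 gives only an enrolment ceiling of 60, so there is no figure of the plan's own to reproduce. Everything below is illustration, except the 28-day window, the three-month recall, the 18-week course, n = 60 and the 0.05 threshold.

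**1. Fibroid volume.** Let T be the total reduction from parent baseline at the end of the extension, and P the reduction already present at entry (both assumed). Change from extension baseline = (1 - T)/(1 - P) - 1.

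| T | P | Change from extension baseline |
|---|---|---|
| 40% | 0% | 0.60/1.00 - 1 = -40.0% |
| 40% | 10% | 0.60/0.90 - 1 = -33.3% |
| 40% | 20% | 0.60/0.80 - 1 = -25.0% |
| 40% | 30% | 0.60/0.70 - 1 = -14.3% |
| 40% | 40% | 0.60/0.60 - 1 = 0.0% |
| 20% | 30% | 0.80/0.70 - 1 = +14.3% |

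The contrasts agree only if nothing carries over. When they differ, the pair is informative: -40% cumulatively with 0% during the extension is what maintained shrinkage looks like.

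**2. UFS-QOL.** Take recall as 90 days and assume continuous active parent dosing up to a gap of w weeks. Share of the entry recall on parent drug = max(0, 90 - 7w)/90.

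- w = 3: 69/90 = 76.7%
- w = 7: 41/90 = 45.6%
- w = 11: 13/90 = 14.4%
- w = 13: 0%, the break point being 90/7 = 12.9 weeks

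At the end of a course, 18 x 7 = 126 days exceeds 90, so that recall lies wholly within the course. Overlap at entry is therefore possible, but w is not in the readable text.

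Suppose further that recall is linear in days, that all 60 women had active parent drug, and that the effect against an untreated state is 0.5 SD. The standardized change from the extension baseline is then 0.5 x 7w/90, capped at 0.5. Power of a paired t-test at two-sided 0.05 is 14.4% at w = 3 (change 0.117) and 96.8% at w = 13 (change 0.500). The range runs from severe loss to none and is set by the unknown gap, so it cannot size the problem.

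**3. PBAC.** Under Section 8.2.1, Course 1 starts within 4 days after bleeding ends at Visit 19 or 24. At selected sites it starts on the first day of bleeding in the next cycle. The 28-day window thus ends off drug with menses returned. Set parent baseline to 100, the entry window to R and the on-drug score to D (assumed). The parent contrast is D/100 - 1 and the extension contrast is D/R - 1.

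- D = 0, R from 60 to 120: both are -100%.
- D = 20: the parent contrast is -80%. The extension contrast is 20/60 - 1 = -67% at R = 60 and 20/120 - 1 = -83% at R = 120.

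The extension contrast can match or exceed the parent contrast. It compares re-treatment with recovery bleeding, not further gain on top of retained benefit.

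**4. Percentage change.** A 10-point fall is 10/60 = 17% from a score of 60 and 10/20 = 50% from 20, so the scale matters in principle. Section 8.1 already lists change for these two endpoints, and the paired tests can be run on scores. A zero PBAC baseline is unlikely in a window that normally follows a menses.

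**The case for a change.** The best case for a change is that it is cheap. Up to two p-values per endpoint carry the same label at 0.05, and no stated rule says which prevails. Rewording before database lock would prevent a choice between them afterwards and would keep maintained benefit from being reported as failure. For fibroid volume and UFS-QOL the mechanism is sound, and the three-month recall does not fit a 28-day baseline. That much stands.

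The natural remedy is to make the parent baseline the sole reference for treatment-effect conclusions, and it does not improve matters. With no control group, that contrast mixes parent treatment, extension treatment and change over time, so the label is no more accurate there. For PBAC it would also demote the comparison closest in time to extension dosing. What survives is a preference for neutral names, cumulative change and change during the extension, which a report author can adopt without any change to what is computed.

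Section 12.3 also calls for a separate SAP, and the Synopsis refers to Study Procedures. Neither is in the readable text, so timing and interpretation may be settled there.

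**Conclusion.** No change to the plan is needed. The wording is loose: in Sections 12.2.4 and 12.2.5 one label covers two contrasts that differ whenever parent-study benefit persists at entry. For PBAC the concern is not shown. Both contrasts are already planned, and reporting them together lets a reader tell maintained benefit from no benefit. Rewording would alter no data, no test and no decision in a study whose primary objective is safety.

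The size cannot be fixed from the documents. In the volume illustration with T = 40%, the extension contrast runs from -40% (no carryover) to 0% (full carryover). In the UFS-QOL illustration, the share of recall on parent drug runs from 76.7% to 0%. Both depend on the assumed carryover, parent-study treatment and off-drug gap. Analysts would be expected to describe the two contrasts for what they are and to claim a controlled treatment effect from neither.

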12.2.1 Demographics and Subject Characteristics

For all subjects included in this study, subject disposition and demographic data will be summarized. Summaries for quantitative variables include the sample size, mean, median, standard deviation, minimum, and maximum. Summaries for categorical variables include the number and percent of patients for each outcome.

12.2.2 Incidence of Amenorrhea

The percentage of subjects who become amenorrheic during the 28 days leading up to the last day of dosing in each course will be determined. The incidence of amenorrhea during the entire course and after the 11th day of the course will also be investigated.

A subject is deemed amenorrheic if they have no bleeding intensity score greater than 1 using the Daily Diary Card in Appendix 2 (spotting not requiring hygiene products) during the period.

12.2.3 Percentage Change in PBAC Scores

The percentage change in PBAC scores over each 28 day period of the course will be recorded and compared to baseline to determine onset of benefit. Additionally PBAC scores will be used to monitor the level of vaginal bleeding during the ODI.

Within treatment group paired t-tests will evaluate treatment effect. While the primary assessment will be after each 18 week treatment course, summaries will be prepared for each of the other visits. If data are missing, a last observation carried forward procedure will be used, including the baseline, if necessary. Non-parametric methods will be employed as appropriate.

12.2.4 Percentage Change in Total and Individual Symptom Severity Scores for the UFSQOL

The UFSQOL has been validated as a three month look back

questionnaire. The survey will be administered at baseline and at the end of each course. Within group paired tests will be used to assess treatment effect. Non-parametric methods will be employed as appropriate. If data are missing, a last observation carried forward procedure will be used, including the baseline, if necessary.

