	The start of the first 18-week course of treatment (Course 1) should commence no later than 4 days after the end of bleeding, i.e. at visit 24 (or Visit 19, see Study Procedures below) of the previous study. Once dosing for Course 1 is stopped, subjects will be followed until menses returns. The start of the second and third 18 week courses of treatment (Courses 2 and 3) will commence no later than 4 days after the end of bleeding in the subject's menses following withdrawal of drug after the previous course has been completed.
	At selected sites subjects will commence dosing on the first day of bleeding in their next menstrual cycle after Visit 19 or Visit 24 (about 3 weeks after V19 or 24). The start of the second and third courses of treatment will start on the first day of bleeding in the subject's second menses following withdrawal of study drug.
	During the ODI, subjects will continue to record study information in the daily paper diary and PBAC charts.
	Any subject who has any 28-day period during treatment (not including the ODIs) without a bleeding score >1 will be deemed to have achieved amenorrhea. Subjects who do not achieve amenorrhea after 8 weeks of treatment will exit the study. After completion of 3 courses of treatment, subjects will be followed through the subsequent menstrual event (recovery menses).
	A DSMB will review any liver safety events (LFTs $\geq 3 \times ULN$ or bilirubin $\geq 2 \times ULN$).
Subject Population:	The study will enroll women who have successfully completed either study ZPV-201 or ZPU-203 and meet eligibility criteria.
Number of Subjects:	Up to about 60 subjects
Number of Sites	Approximately 10 sites
Study Duration:	Total participation in the study is approximately 13 months.

:	
Study Endpoints	Endpoints will be:
	• Percentage of subjects who become amenorrheic
	• Change in UFS-QOL Symptom Severity score comparing to the previous study baseline and study baseline
	• Change in the individual UFS-QOL sub scores
	Change in PBAC scores
	• Percentage change from parent study baseline and study baseline in total uterine fibroid volume measured by MRI
	• Incidence of significant adverse events
	Changes in physical examination results
	Changes in clinical laboratory results
	Changes in liver function to values
	• Unexpected or excessive vaginal bleeding
	Endometrial thickness assessed using vaginal ultrasounds
	• Change in number and intensity of bleeding days over the course of the treatment and ODI periods

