	• Pathology of the endometrium assessed by biopsies.

Statistical Methods:	Summaries for quantitative variables include the sample size, mean, median, standard deviation, minimum, and maximum. Summaries for categorical variables include the number and percent of patients for each outcome.
	Continuous efficacy endpoints, such as the change from baseline in uterine tumor volumes will assess treatment effect using a within- group t-test or appropriate non-parametric technique. The percentage of subjects becoming amenorrheic will be determined.

[figure not shown]

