8. TRIAL DESIGN

8.1 Study Endpoints

- Percentage of subjects who become amenorrheic over the course of the study
- Change in UFS-QOL Symptom Severity Score comparing to the previous study baseline and study baseline
- Change in the individual UFS-QOL subscores over the course of the study
- Change in PBAC scores over the course of the study
- Percentage change from parent study baseline and study baseline in total uterine fibroid volume measured by MRI

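### Section 12.2.4 puts the UFS-QOL analysis on a percentage scale although the endpoint lists define it as change, and it does not clearly specify an analysis of the UFS-QOL subscores

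*Combined protocol and SAP*

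**What the plan says.** Section 8.1 lists two UFS-QOL endpoints: "Change in UFS-QOL Symptom Severity Score comparing to the previous study baseline and study baseline" and "Change in the individual UFS-QOL subscores over the course of the study". The synopsis carries the same pair, the second as "Change in the individual UFS-QOL sub scores". Fibroid volume, in the same lists, is worded differently: "Percentage change from parent study baseline and study baseline in total uterine fibroid volume measured by MRI".

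Section 12.2.4 is the only part of Section 12 on this questionnaire. Its heading is "Percentage Change in Total and Individual Symptom Severity Scores for the UFSQOL". The body gives the recall period, the times of administration, the type of test ("Within group paired tests will be used to assess treatment effect"), a non-parametric fallback and last observation carried forward. It names neither a score nor a scale.

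Section 12.2 sets up two baselines, one from the parent study and one from the 28 days before the extension, and adds: "Reference to baseline in this section refers to each baseline definition".

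**The concern.** The heading of 12.2.4 is the only place where the plan says what is to be analysed for this questionnaire, and it departs from the endpoint list in two ways. It changes the scale from change to percentage change. It also refers to Symptom Severity scores, whereas 8.1 lists the subscores as a separate endpoint.

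The scale matters more here than in a first-treatment trial because one of the two denominators is measured after a parent study. A ratio to a small questionnaire score is unstable, and a ratio to zero does not exist. At stake are a mean that could point the opposite way from the change in score points, women without a value for whom no rule is given, and a listed endpoint whose analysis is left to interpretation.

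**Working it through.** The plan gives no expected UFS-QOL score, SD, score range or power, so there is no figure of its own to reproduce. The check is a comparison of wording followed by arithmetic on assumed scores.

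**Wording**

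- Symptom Severity: change in the synopsis and 8.1; percentage change in the heading of 12.2.4.
- Individual subscores: change in the synopsis and 8.1; not named in Section 12, unless the word for individual scores in the 12.2.4 heading is meant to cover them.
- Fibroid volume: percentage change in the synopsis, 8.1 and 12.2.5, so here list and analysis agree.
- Zero or very low baseline: no rule. Carrying an observation forward (12.2.4) and imputing no change when there are no post-baseline data (12.3) fill in missing values. Neither repairs a zero denominator.

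**Are low extension baselines plausible?** Under 8.2.1, women enter at Visit 24 of the parent study unless they failed to achieve amenorrhea, in which case they may enter at Visit 19. In 6.1 the sponsor links symptom relief directly to amenorrhea. A mix of lower and higher baselines is therefore plausible, but no score is reported.

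**Arithmetic.** Percentage change = 100 × (follow-up − baseline) / baseline. All scores are assumed, with lower taken as better.

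- Two women, 60 to 20 and 4 to 12. Points: −40 and +8, mean (−40 + 8)/2 = −16. Percentages: −66.7% and +200%, mean (−66.7 + 200)/2 = +66.7%.
- Four women, baselines 60, 50, 40, 5 and follow-ups 45, 40, 32, 15. Points: −15, −10, −8, +10, mean −23/4 = −5.75. Percentages: −25, −20, −20, +200, mean 135/4 = +33.75%.
- A 5-point rise is 8.3% at a baseline of 60, 25% at 20, 50% at 10, 100% at 5 and 250% at 2. At 0 it is undefined.

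**Simulation with no true change.** Assumptions, none from the documents except the ceiling of 60 women (12.1) and the two-sided 0.05 level (12.3): score bounded 0 to 100 and rounded to whole points, measurement SD 7 on each occasion, 2,000 runs, one-sample t-test, zero baselines left out of the percentage analysis.

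| Assumed baseline mean / SD | Mean percentage change | Share undefined |
|---|---|---|
| 60 / 20 | +2.7% | 0.2% |
| 40 / 20 | +7.9% | 2.5% |
| 25 / 15 | +16.1% | 5.7% |
| 15 / 12 | +24.5% | 12.5% |
| 10 / 10 | +28.3% | 17.9% |

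Across these rows the percentage-change test rejected upward in 5.5% to 7.9% of runs and downward in 0.4% to 0.9%, against a nominal 2.5% each way. Change in points had a mean between −0.04 and +0.02, an overall rejection rate of 4.4% to 5.1%, and no undefined values.

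The upward drift comes from error in the denominator: a baseline that is low by chance inflates the ratio. Where lower is better, the drift hides benefit. For any score where higher is better, it would flatter the drug.

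**The case against.** The best case for the plan is that this is loose drafting. The percentage appears only in the heading of 12.2.4, whereas the bodies of 12.2.3 and 12.2.5 repeat it, and a paired test can be run on raw scores. The protocol is also loose elsewhere: 8.1 lists PBAC as change while 12.2.3 analyses percentage change. Rank-based methods are allowed and would limit the pull of a few extreme ratios. A separate SAP is still to come (12.3), and scoring detail may sit in pages that are not public. The primary objective is safety, and the study is open-label and not powered.

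Much of this is fair, and it limits the point. It does not remove it. With no variable in the body, the heading is what a programmer would follow. Rank methods do not create a value where the baseline is zero. The SAP author would still face two conflicting protocol statements.

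Three stronger readings are tempting, and the documents do not support them:

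- A reader might infer that the subscores are not analysed at all. The heading's mention of individual scores may be meant to include them, the body of 12.2.4 does not restrict the tests to Symptom Severity, and the synopsis has a general provision beginning "Continuous efficacy endpoints, such as the change from baseline in uterine tumor volumes will assess treatment effect using a", which names a within-group t-test or a non-parametric alternative.
- A reader might infer that many women start the extension with low scores. No UFS-QOL value is given. Women start after bleeding has returned, and those entering at Visit 19 had not achieved amenorrhea.
- A reader might infer that women with a zero baseline would be dropped and are the best parent-study responders. No zero score is documented, and no exclusion rule is stated.

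**Conclusion.** The point holds in a limited form. Endpoint list and analysis section disagree on the scale, and the subscore analysis is not clearly specified; both can be read directly from the text. That percentage change is undefined at zero and unstable at low baselines is arithmetic.

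The size in this trial is unknown. On the assumptions above, with no true change, the distortion runs from small (+2.7% at an assumed baseline mean of 60) to large (+28.3%, with 17.9% of values undefined, at a mean of 10). The sign reversals use scores chosen to show that reversal can happen; they do not show that it will.

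Since UFS-QOL is one of several listed efficacy endpoints in a study whose primary objective is safety, this should be corrected but does not threaten the main purpose of the trial. It is more than a missing detail, because change in points, which 8.1 already words, is a better variable than the one in the heading.

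**What to change.** Rewrite 12.2.4, including its heading, so that change in score points from each of the two baselines is the analysis variable for the Symptom Severity Score and for each UFS-QOL subscore, with the subscores listed by name. Keep the within-group paired tests and the non-parametric alternative. If percentage change is retained, present it only descriptively, against the parent-study baseline, and state how a zero baseline is shown. Carry the same definitions into the SAP. As the study is open-label and scores are visible as they accrue, the choice is best fixed now.

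The cost is the rewording and a few extra tables. No new data, visits or subjects are needed.
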